# Appendix D: Lee cGVHD Symptom Score

By circling one number per line, please indicate how much you have been bothered by the following problems in the past 7 days: (Lee et al. 2002)

Skin		Not at all	Slightly	Moderately	Quite a bit	Extremely
1.	Abnormal skin color	0	1	2	3	4
2.	Rashes	0	1	2	3	4
3.	Thickened skin	0	1	2	3	4
4.	Sores on skin	0	1	2	3	4
5.	Itchy skin	0	1	2	3	4
Eyes a	nd Mouth	Not at all	Slightly	Moderately	Quite a bit	Extremely
6.	Dry eyes	0	1	2	3	4
7.	Need to use eye drops frequently	0	1	2	3	4
8.	Difficulty seeing clearly	0	1	2	3	4
9.	Need to avoid certain foods due to mouth pain	0	1	2	3	4
10.	Ulcers in mouth	0	1	2	3	4
11.	Receiving nutrition from and intravenous line or feeding tube	0	1	2	3	4
Breath	ing	Not at all	Slightly	Moderately	Quite a bit	Extremely
12.	Frequent cough	0	1	2	3	4
13.	Colored sputum	0	1	2	3	4
14.	Shortness of breath with exercise	0	1	2	3	4
15.	Shortness of breath at rest	0	1	2	3	4
16.	Need to use oxygen	0	1	2	3	4
Eating	and Digestion	Not at all	Slightly	Moderately	Quite a bit	Extremely
17.	Difficulty swallowing solid foods	0	1	2	3	4
18.	Difficulty swallowing liquids	0	1	2	3	4
19.	Vomiting	0	1	2	3	4
20.	Weight loss	0	1	2	3	4
Muscle	es and Joints	Not at all	Slightly	Moderately	Quite a bit	Extremely
21.	Joint and muscle aches	0	1	2	3	4
22.	Limited joint movement	0	1	2	3	4
23.	Muscle cramps	0	1	2	3	4
24.	Weak muscled	0	1	2	3	4
Energ	7	Not at all	Slightly	Moderately	Quite a bit	Extremely
25.	Loss of energy	0	1	2	3	4
26.	Need to sleep more/take naps	0	1	2	3	4
27.	Fevers	0	1	2	3	4
Menta	l and Emotional	Not at all	Slightly	Moderately	Quite a bit	Extremely
28.	Depression	0	1	2	3	4
29.	Anxiety	0	1	2	3	4
30.	Difficulty sleeping	0	1	2	3	4

# Appendix E: Karnofsky Performance Scale

Score	Description	
100	Normal, no complaints, no evidence of disease	
90	Able to carry on normal activity	
80	Normal activity with effort	
70	Cares for self; unable to carry on normal activity or to do active work	
60	60 Requires occasional assistance but is able to care for most needs	
50	Requires considerable assistance and frequent medical care	
40	Disabled; requires special care and assistance	
30	Severely disabled; hospitalization indicated; death not imminent	
20	Very sick; hospitalization indicated; death not imminent	
10	Moribund; fatal processes progressing rapidly	

Scores 80 to 100: able to carry on normal activity; no special care is needed

Scores 50 to 70: unable to work; able to live at home and care for most personal needs; a varying degree of assistance needed Scores 10 to 40: unable to care for self; requires equivalent of institutional or hospice care; disease may be progressing rapidly Source: Karnofsky et al. 1949

## Appendix F: Equations to Predict Glomerular Filtration Rate (MDRD-4)

### 4-Variable Modification of Diet in Renal Disease (MDRD-4) Equation

# High Level Formula for Black or African-American Males:

Estimated GFR =  $175 \times (Creatinine^{-1.154}) \times (Age^{-0.203}) \times 1.212$ 

High Level Formula for Males NOT Black or African-American (any other option):

Estimated GFR =  $175 \times (\text{Creatinine}^{-1.154}) \times (\text{Age}^{-0.203})$ 

High Level Formula for Black or African-American Females:

Estimated GFR =  $175 \times (Creatinine^{-1.154}) \times (Age^{-0.203}) \times 1.212 \times 0.742$ 

High Level Formula for Females NOT Black or African-American (any other option):

Estimated GFR =  $175 \times (\text{Creatinine}^{-1.154}) \times (\text{Age}^{-0.203}) \times 0.742$ 

Levey et al. 2006

## Appendix G: Determining Relationship of AEs to Study Drug

#### 1 NOT RELATED

This category applies to those AEs which, after careful medical consideration, are clearly felt to be due to extraneous causes (e.g., disease, environment, etc.) that are unrelated to the administration of study drug.

#### 2 UNLIKELY RELATED (must have first 2)

This category applies to those AEs which, after careful medical consideration, are felt unlikely to be related to the administration of the study drug. The relationship of an AE to the study drug can be considered unlikely if:

- It does not follow a reasonable temporal sequence from administration of the drug.
- It could readily have been a result of the subject's clinical state, environmental or toxic factors, or other modes of therapy administered to the subject.
- It does not follow a known response pattern to the suspected drug.
- It does not reappear or worsen when the drug is re-administered.

### **3 POSSIBLY RELATED** (must have first 2)

This category applies to those AEs which, after careful medical consideration, are felt unlikely to be related to the administration of the study drug, but the possibility cannot be ruled out with certainty. The relationship of an AE to the study drug can be considered possible if:

- It follows a reasonable temporal sequence from administration of the drug.
- It could readily have been a result of the subject's clinical state, environmental or toxic factors, or other modes of therapy administered to the subject.
- It follows a known response pattern to the suspected drug.

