### 5.10 Dose Modification Guidelines

Any clinically significant toxicity will necessitate consideration of either a pause or cessation of therapy. Guidelines for management of treatment-emergent toxicities in subjects receiving belumosudil are outlined in Table 5. When dose reduction is necessary, the dose should be decreased as shown in Table 6.

Table 5. Guidelines for the Management of TEAEs with Belumosudil Treatment

Toxicity	Recommended Action		
Grade 4 organ toxicities considered at least possibly related to belumosudil	Discontinue belumosudil		
Grade ≥ 3 LFTs (AST, ALT or total bilirubin) regardless of attribution to belumosudil	
 
Hold belumosudil dosing until resolution to Grade 1 or below levels
 
Consider resuming belumosudil. If resuming, then resume at 1 dose decrement
 
If toxicity recurs, discontinue belumosudil
 
		
Other Grade ≥3 clinically significant toxicities considered at least possibly related to belumosudil	Hold belumosudil dosing until toxicity has resolved to Grade 1 or below then consider resuming belumosudil. If resuming, then resume at 1 dose decrement     If toxicity recurs, hold dose as above then consider resuming belumosudil at one dose decrement		

ALT = alanine aminotransferase; AST = aspartate aminotransferase; eCRF = electronic case report form; LFT = liver function test; TEAE = treatment-emergent adverse event

Dose interruption for up to 14 days for toxicity management is permitted. Subjects requiring pauses of more than 14 days will be discontinued from the study unless approved by the medical monitor.

Table 6. Belumosudil Dose Decrements

Belumosudil Dose	Dose Reduction	
400 mg QD	200 mg QD	
200 mg BID	200 mg QD	
200 mg QD	200 mg QOD	

BID = twice daily; QD = once daily; QOD = once every other day

If the reduced dose of belumosudil is tolerated for 1 month, the dose may be escalated to the previous dose.

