### 7.3.3 Relationship to Study Drug

The Investigator will attempt to assess the relationship of the event to study drug using a 5-point scale (not related, unlikely-related, possibly related, probably related, or definitely related; (Appendix G: Determining Relationship of AEs to Study Drug).

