### 7.3.5.2 SAE Information to be Provided by the Investigator

The SAEs for all enrolled subjects must be recorded on the SAE form (during study participation). This requirement includes all SAEs that occur after informed consent and through the 28-day Follow-up Visit at 28 days after last dose of study drug. In addition, any SAEs that are assessed as at least possibly related to study drug by the Investigator, even if the SAE occurs more than 28 days after the last dose of study drug, must be reported to the Kadmon Pharmacovigilance (or designee) as described below:

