#### 4 **PROBABLY RELATED** (must have first 3)

This category applies to those AEs which, after careful medical consideration, are felt with a high degree of certainty to be related to the administration of the study drug. The relationship of an AE to the study drug can be considered probable if:

- It follows a reasonable temporal sequence from administration of the drug.
- It could not be reasonably explained by the known characteristics of the subject's clinical state, environmental or toxic factors or other modes of therapy administered to the subject.
- It disappears or decreases upon cessation of drug or reduction in dose.\*
- It follows a known response pattern to the suspected drug.

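### Read literally, Appendix G has no causality category for a well-timed event with no other reasonable explanation and no dechallenge result

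*Protocol*

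**What the plan says.** Protocol Section 7.3.3 sets the method: "The Investigator will attempt to assess the relationship of the event to study drug using a 5-point scale", with the five categories defined in Appendix G. Four of them carry a list of criteria and a note of how many are mandatory.

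- *Not related* has no list. Its lead sentence covers events "clearly felt to be due to extraneous causes".
- *Unlikely related* (first two mandatory) opens with "It does not follow a reasonable temporal sequence from administration of the drug" and also needs a ready alternative cause.
- *Possibly related* (first two mandatory) needs plausible timing and "It could readily have been a result of the subject's clinical state, environmental or toxic factors". Its lead sentence describes events "felt unlikely to be related to the administration of the study drug, but the possibility cannot be ruled out with certainty".
- *Probably related* (first three mandatory) needs plausible timing, no reasonable alternative explanation, and "It disappears or decreases upon cessation of drug or reduction in dose".
- *Definitely related* (first three mandatory) needs the same plus recurrence on rechallenge.

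A footnote to the third criterion of the last two categories allows exceptions for an event that persists after the drug is discontinued although relatedness is clear.

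The rating is then used elsewhere. In Table 5 (Section 5.10), the Grade 4 organ toxicity row and the row for other Grade 3 or higher "clinically significant toxicities considered at least possibly related to belumosudil" depend on it. For SAEs more than 28 days after the last dose, Section 7.3.5.2 requires reporting of "any SAEs that are assessed as at least possibly related to study drug by the Investigator". Protocol Section 9.9 and SAP Section 3.8.1 tabulate related events.

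**The concern.** An absent alternative explanation should, other things equal, raise suspicion of the drug. In Appendix G it removes the event from 'possibly related', and the next category up cannot be reached without a dechallenge result. That result is often missing: the drug was continued unchanged, the subject died before any response to stopping could be seen, or the report is due before the outcome is known.

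The rating is also requested at moments when dechallenge information usually cannot exist. Table 5 needs it before the drug is held. An SAE that begins more than 28 days after the last dose has no ordinary dechallenge to observe. Section 7.3.5.2 lists the causality assessment in the minimum SAE information, and the form is due within 24 hours.

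At stake are consistent ratings across about 20 sites, and two protocol triggers that rest on a category the written criteria do not supply for this kind of event. The study is open-label and every treatment group receives belumosudil, so the relatedness tables are one of the main ways to separate drug effects from background illness.

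**Working it through.** The plan gives no figure to reproduce, because this is a question of logical coverage. The check sets the mandatory criteria side by side and looks for combinations that none of them covers.

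**1. Mandatory criteria (Appendix G)**

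| Category | Timing | Other explanation | Dechallenge |
|---|---|---|---|
| Not related | not listed | clear extraneous cause (lead sentence) | not listed |
| Unlikely | implausible | readily available | not mandatory |
| Possibly | plausible | readily available | not mandatory |
| Probably | plausible | none reasonable | improvement |
| Definitely | plausible, or drug levels shown in the body | none reasonable | improvement, then recurrence on rechallenge |

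**2. The profile in question: plausible timing, no reasonable alternative, no dechallenge result**

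- Not related: fails, as there is no extraneous cause.
- Unlikely: fails on timing and on alternative cause.
- Possibly: fails on alternative cause.
- Probably: fails on dechallenge.
- Definitely: fails on dechallenge and rechallenge.

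No category fits. Change one fact, so that a ready alternative cause exists, and the event meets both mandatory criteria for 'possibly'. That is the inversion.

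**3. Full enumeration**

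Timing (plausible, implausible) × alternative cause (ready, none reasonable) × dechallenge (positive, negative, none) gives 2 × 2 × 3 = 12 combinations. Rechallenge is taken as not done. 'Not related' is left out of the count because it has no mandatory list.

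- Plausible timing, ready alternative: 3 combinations, all 'possibly'.
- Implausible timing, ready alternative: 3 combinations, all 'unlikely'.
- Plausible timing, no alternative, positive dechallenge: 1 combination, 'probably'.
- Covered on the literal text: 3 + 3 + 1 = 7. Unclassified: 12 − 7 = 5.
- With the footnote applied to negative dechallenge, one more combination is covered: 7 + 1 = 8. Unclassified: 12 − 8 = 4.

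The profile in step 2 is among the unclassified on both counts. The other three that remain have implausible timing and no alternative explanation. They are a separate hole of less concern, because their timing argues against the drug. These are counts of combinations, not of events.

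**4. Why the footnote does not close the gap**

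It presupposes that the drug was discontinued and that the event was then seen to persist. It is silent on a drug that was continued and on an outcome that is pending or can never be observed.

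**5. What does and does not depend on the rating**

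| Use | Depends on the rating? |
|---|---|
| Table 5, Grade 4 organ toxicity | yes |
| Table 5, other Grade 3 or higher toxicity | yes |
| Table 5, AST, ALT or bilirubin | no, applies whatever the attribution |
| SAE on treatment or within 28 days (7.3.5.1) | no |
| SAE beyond 28 days (7.3.5.2) | yes |
| SAE beyond 28 days (7.3.5.1) | looser wording, tied to belief that the drug was responsible |
| Related-event tables (Protocol 9.9, SAP 3.8.1) | yes |
| All-TEAE and serious-TEAE tables (SAP 3.8.1) | no |

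**The case against.** The best reply is that Appendix G guides medical judgement and is not an algorithm. Section 7.3.3 speaks of an attempt to assess, and each category is prefaced by careful consideration. An investigator facing this profile could reasonably choose 'possibly' or 'probably'. In KD025-213 one fatal event, multiple organ dysfunction syndrome, was considered related (Section 1.4.2), so a fatal outcome did not prevent a related rating there. The documents do not say whether that study used the same criteria.

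The consequences are also bounded. Early SAEs are reported regardless of relationship, follow-up SAE reports are required, Table 5 is headed as guidelines, and Section 4.6 lets the investigator withdraw treatment that is judged detrimental. If the field is left blank, SAP Section 3.1.6.1 counts the event as related, though only in the frequency tables. The lead sentence for 'possibly' overlaps with 'unlikely' but goes on to say that a drug effect cannot be excluded, so that overlap alone is a weak complaint.

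Most of this stands, and it limits the point. It does not remove it: the criteria are labelled as mandatory, and asking sites to override them invites different answers at different sites.

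A reader might infer three stronger things, none of which the documents support:

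- *That the most suspicious events are excluded.* Events with positive dechallenge or rechallenge are more suspicious, and they are classified.
- *That related events will be under-called.* The profile does not fit 'not related' either. Raters may go up, down or leave a blank, so the direction is unknown.
- *That the parent-study totals measure the problem.* SAEs in 45/132 and 23/54 subjects, and fatal TEAEs in 5 and 4, are overall counts. In transplant recipients with cGVHD on other immunosuppressants, many events will have a ready alternative explanation and so qualify as 'possibly'.

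**Conclusion.** The gap is real on the text. One clinically plausible profile has no category under the mandatory criteria, with or without the footnote, and it ranks below an otherwise identical event that has a competing explanation. It bears on two of the three Table 5 rows, on SAE reporting beyond 28 days under Section 7.3.5.2, and on the related-event tables. It does not bear on earlier SAEs or on the liver-test row.

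The conclusion rests on reading the must-have notes as binding and on treating the alternative explanation as either readily available or not reasonable. An in-between case would fail both versions of that criterion, so relaxing this assumption would not shrink the gap. The number of events affected and the direction of any bias cannot be obtained from the documents. This should be corrected because the correction is cheap, not because harm to the results has been shown.

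**What to change.** Keep the existing criteria and add one sentence to Appendix G: when dechallenge was not done, is not possible or is not yet known, an event with plausible timing and no other reasonable explanation is rated at least 'possibly related', and the rating is updated at follow-up.

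Then reconcile the category definitions with the triggers in Table 5 and Sections 7.3.5.1 and 7.3.5.2, so that the two reporting sections use the same test for late SAEs. The actions in Table 5 stay as written. Because the rating feeds that table, the sponsor's clinical team should confirm that the clarified category matches what the table intends.

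Making plausible timing the only requirement for 'possibly related' would also close the gap, but it is not recommended here. Under continuous dosing for up to two further years, it could relabel many on-treatment events that have an obvious other cause.

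The cost is a short amendment and a site training note. The count of related AEs may rise, by an amount the documents do not allow anyone to estimate.

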#### 4 **PROBABLY RELATED** (must have first 3)

This category applies to those AEs which, after careful medical consideration, are felt with a high degree of certainty to be related to the administration of the study drug. The relationship of an AE to the study drug can be considered probable if:

- It follows a reasonable temporal sequence from administration of the drug.
- It could not be reasonably explained by the known characteristics of the subject's clinical state, environmental or toxic factors or other modes of therapy administered to the subject.
- It disappears or decreases upon cessation of drug or reduction in dose.\*
- It follows a known response pattern to the suspected drug.

### 5 **DEFINITELY RELATED** (must have first 3)

This category applies to those AEs, which, after careful medical consideration, are felt to be related to the administration of the study drug. The relationship of an AE to the study drug can be considered related if:

- It follows a reasonable temporal sequence from administration of the drug or drug levels have been established in body fluids or tissues.
- It could not be reasonably explained by the known characteristics of the subject's clinical state, environmental or toxic factors or other modes of therapy administered to the subject.
- It disappears or decreases upon cessation of drug or reduction on dose and appears upon rechallenge.\*
- It follows a known response pattern to the suspected drug.

Source: Adapted from Cobert B 2012(30)

\*There are exceptions when an AE does not disappear upon discontinuation of the drug, yet drug relatedness clearly exists.

# Appendix H: Drugs that Induce CYP3A4

This is not a comprehensive list, and all concomitant medications should be evaluated for possible interactions with belumosudil.

Table 8. Examples of Clinical Inducers of CYP3A4

Strong Inducer	Moderate Inducer	Weak Inducer
Apalutamide	Bosentan	Armodafinil
Carbamazepine	Efavirenz	Modafinil
Enzalutamide	Etravirine	Rufinamide
Mitotane	Phenobarbital	
Phenytoin	Primidone	
Rifampin		
St. John's wort		

Source: FDA. Drug Development and Drug Interactions.

# Appendix I: Drugs That Induce and Inhibit CYP1A2

This is not a comprehensive list, and all concomitant medications should be evaluated for possible interactions with belumosudil.

Table 9. Examples of Clinical Inducers/Inhibitors of CYP1A2

	Strong	Moderate	Weak
Inducers	Rifampin	Phenytoin	
		Rifampin	
		Ritonavir	
		Smoking	
		Teriflunomide	
Inhibitors	Ciprofloxacin	Methoxsalen	Acyclovir
	Enoxacin	Mexiletine	Allopurinol
	Fluvoxamine	Oral contraceptives	Cimetidine
			Peginterferon α-2a
			Piperine
			Zileuton

Source: FDA. Drug Development and Drug Interactions.

 $https://www.fda.gov/drugs/developmentapproval process/development resources/drug interactions labeling/ucm 093664. htm Accessed 25 Jun 2021 \end{tabular} Accessed 25 Jun 2021 \end{tabular}$ 

# Appendix J: Drugs That Prolong QTc

This is not a comprehensive list, and all concomitant medications should be evaluated for possible interactions with belumosudil.

Table 10. Examples of Drugs that Prolong QTc

	Generic Name
Aclarubicin	Iloperidone
• Amiodarone	
 
Levofloxacin
 

 
Anagrelide
 
	
 
Levomepromazine
 

Arsenic trioxide	
 
Levomethadyl acetate
 

Astemizole	
 
Levosulpiride
 

Azithromycin	Mesoridazine
Bepridil	
 
Methadone
 

Chloroquine	
 
Moxifloxacin
 

Chlorpromazine	
 
Ondansetron
 

Cilostazol	
 
Oxaliplatin
 

Ciprofloxacin	Papaverine HCl
Cisapride	Pentamidine
Citalopram	Pimozide
Clarithromycin	
 
Probucol
 

Disopyramide	
 
Procainamide
 

Dofetilide	
 
Propofol
 

Domperidone	Quinidine
Donepezil	
 
Roxithromycin
 

Dronedarone	
 
Sevoflurane
 

Droperidol	
 
Sotalol
 

Erythromycin	
 
Sparfloxacin
 

Escitalopram	Sulpiride
Flecainide	
 
Sultopride
 

Fluconazole	Terfenadine
Gatifloxacin	Terlipressin
Grepafloxacin	Terodiline
Halofantrine	Thioridazine
Haloperidol	Vandetanib
Ibogaine	
Ibutilide	

Source: https://crediblemeds.org/pdftemp/pdf/CombinedList.pdf Accessed 11 May 2020

## **Appendix K: Prednisone Dose Equivalents**

Change in corticosteroid doses will be analyzed by using prednisone dose equivalents. If subjects are not using prednisone as the systemic corticosteroid, then the prednisone dose equivalent will be determined according to following conversion ratios.

One mg of prednisone is equivalent to:

- 4.0 mg hydrocortisone
- 0.8 mg Methylprednisolone
- 0.15 mg Dexamethasone
- 1.0 mg Prednisolone
- 0.8 mg Triamcinolone

Source: Liu D et al. 2013(33)

CM	Concomitant Medication
CR	Complete Response
CRF	Case Report Form
CTCAE	Common Terminology Criteria for Adverse Events
DOR	Duration of Responses
ECG	Electrocardiogram
FEV1	Forced Expiratory Volume in One Second
FFS	Failure Free Survival
ICF	Informed Consent Form
ICH	International Conference on Harmonisation
KPS	Karnofsky Performance Scale
LR	Lack of Response
LSS	Lee Symptom Scale Score
LTFU	Long-term Follow-up
MDRD-4	Modification of Diet in Renal Disease
MedDRA	Medical Dictionary for Regulatory Activities
NE	Not Evaluable
NIH	National Institutes of Health
OS	Overall Survival
PFT	Pulmonary Function Test
PR	Partial Response
PT	Preferred Term
QD	Every day
QTcF	Corrected QT interval using Fridericia's formula
SAP	Statistical Analysis Plan
SOC	System Organ Class
TEAE	Treatment-emergent Adverse Event
TTNT	Time to Next Treatment

